3.3.2 Exclusion Criteria

1. Target Disease Exceptions

- a) Active brain metastases or leptomeningeal metastases. Subjects with brain metastases are eligible if these have been treated and there is no magnetic resonance imaging (MRI - except where contraindicated in which computed tomography (CT) scan is acceptable) evidence of progression for at least 8 weeks after treatment is complete and within 28 days prior to first dose of study drug administration. There must also be no requirement for immunosuppressive doses of systemic corticosteroids (> 10 mg/day prednisone equivalents) for at least 2 weeks prior to study drug administration.
- b) Ocular melanoma.

2. Medical History and Concurrent Disease

- a) Prior active malignancy within the previous 3 years except for locally curable cancers that have been apparently cured, such as basal or squamous cell skin cancer, superficial bladder cancer, or carcinoma in situ of the prostate, cervix, or breast
- b) Subjects with an active, known or suspected autoimmune disease. Subjects with Type I diabetes mellitus, hypothyroidism only requiring hormone replacement, skin disorders (such as vitiligo, psoriasis, or alopecia) not requiring systemic treatment, or conditions not expected to recur in the absence of an external trigger are permitted to enroll.

- c) Subjects with a condition requiring systemic treatment with either corticosteroids (> 10 mg daily prednisone equivalent) or other immunosuppressive medications within 14 days of randomization. Inhaled or topical steroids, and adrenal replacement steroid doses > 10 mg daily prednisone equivalent, are permitted in the absence of active autoimmune disease.
- d) Prior treatment with an anti-PD-1, anti-PD-L1, anti-PD-L2, anti-CD37, anti-CTLA-4 antibody, or any other antibody or drug specifically targeting T-cell costimulation or immune checkpoint pathways. This includes utilization of these agents in the adjuvant, neo-adjuvant, and metastatic melanoma setting.
- e) Subjects with interstitial lung disease that is symptomatic or may interfere with the detection or management of suspected drug-related pulmonary toxicity
- f) Known history of testing positive for human immunodeficiency virus (HIV) or known acquired immunodeficiency syndrome (AIDS)
- g) Any serious or uncontrolled medical disorder that, in the opinion of the investigator, may increase the risk associated with study participation or study drug administration, impair the ability of the subject to receive protocol therapy, or interfere with the interpretation of study results.

3. Physical and Laboratory Test Findings

- a) Any positive test for hepatitis B virus or hepatitis C virus indicating acute or chronic infection

4. Allergies and Adverse Drug Reaction

- a) History of allergy or hypersensitivity to study drug components

5. Other Exclusion Criteria

- a) Prisoners or subjects who are involuntarily incarcerated. (Note: under certain specific circumstances, a person who has been imprisoned may be included or permitted to continue as a subject. Strict conditions apply and Bristol-Myers Squibb approval is required.
- b) Subjects who are compulsorily detained for treatment of either a psychiatric or physical (eg, infectious disease) illness.

Eligibility criteria for this study have been carefully considered to ensure the safety of the study subjects and that the results of the study can be used. It is imperative that subjects fully meet all eligibility criteria.

3.3.3 Women of Childbearing Potential

Women of childbearing potential (WOCBP) is defined as any female who has experienced menarche and who has not undergone surgical sterilization (hysterectomy or bilateral oophorectomy) and is not postmenopausal. Menopause is defined as 12 months of amenorrhea in a woman over age 45 years in the absence of other biological or physiological causes. In addition, females under the age of 55 years must have a serum follicle stimulating hormone, (FSH) level > 40 mIU/mL to confirm menopause.

Females treated with hormone replacement therapy, (HRT) are likely to have artificially suppressed FSH levels and may require a washout period in order to obtain a physiologic FSH level. The duration of the washout period is a function of the type of HRT used. The duration of the washout period below are suggested guidelines and the investigators should use their judgement in checking serum FSH levels.

- 1 week minimum for vaginal hormonal products (rings, creams, gels)
- 4 week minimum for transdermal products
- 8 week minimum for oral products

Other parenteral products may require washout periods as long as 6 months. If the serum FSH level is >40 mIU/ml at any time during the washout period, the woman can be considered postmenopausal.

3.4 Concomitant Treatments

[REDACTED]

[REDACTED]

[REDACTED]

[REDACTED]

[REDACTED] alliative radiation therapy, or standard or investigational agents for treatment of cancer).

[REDACTED]

[REDACTED]

[REDACTED]

[REDACTED]

[REDACTED]

[REDACTED]

[REDACTED]

3.5 Discontinuation of Subjects following any Treatment with Study Drug

Subjects MUST discontinue investigational product (and non-investigational product at the discretion of the investigator) for any of the following reasons:

- Subject's request to stop study treatment
- Any clinical adverse event, laboratory abnormality or intercurrent illness which, in the opinion of the investigator, indicates that continued participation in the study is not in the best interest of the subject
- Termination of the study by BMS
- Loss of ability to freely provide consent through imprisonment or involuntarily incarceration for treatment of either a psychiatric or physical (eg, infectious disease) illness
- Unblinding a subject for any reason (emergency or non-emergency)
- Pregnancy.

In the case of pregnancy, the investigator must immediately notify the BMS Medical Monitor/designee of this event. In the event a normal healthy female subject becomes pregnant during a clinical trial, the study drug must be discontinued immediately. In most cases, the study drug will be permanently discontinued in an appropriate manner (eg, dose tapering if necessary for subject safety). Please call the BMS Medical Monitor within 24 hours of awareness of the pregnancy. If the investigator determines a possible favorable benefit/risk ratio that warrants continuation of study drug, a discussion between the investigator and the BMS Medical Monitor/designee must occur.

All subjects who discontinue study drug should comply with protocol specified follow-up procedures as outlined in [Section 5](#). The only exception to this requirement is when a subject withdraws consent for all study procedures including post-treatment study follow-up or loses the ability to consent freely (ie, is imprisoned or involuntarily incarcerated for the treatment of either a psychiatric or physical illness).

Please also refer to Discontinuation Criteria in [Section 4.4.4](#).

If study drug is discontinued prior to the subject's completion of the study, the reason for the discontinuation must be documented in the subject's medical records and entered on the appropriate case report form (CRF) page.

3.6 Post Study Drug Study Follow up

In this study, overall survival is a key endpoint of the study. Post study follow-up is of critical importance and is essential to preserving subject safety and the integrity of the study. Subjects who discontinue study drug must continue to be followed for collection of outcome and/or survival follow-up data as required and in line with [Section 5](#) until death or the conclusion of the study.

BMS may request that survival data be collected on all treated/randomized subjects outside of the protocol defined window ([Table 5.1-1](#)). At the time of this request, each subject will be contacted to determine their survival status unless the subject has withdrawn consent for all contacts or is lost to follow-up.

3.6.1 Withdrawal of Consent

Subjects who request to discontinue study drug will remain in the study and must continue to be followed for protocol specified follow-up procedures. The only exception to this is when a subject specifically withdraws consent for any further contact with him/her or persons previously authorized by subject to provide this information. Subjects should notify the investigator of the decision to withdraw consent from future follow-up **in writing**, whenever possible. The withdrawal of consent should be explained in detail in the medical records by the investigator, as to whether the withdrawal is from further treatment with study drug only or also from study procedures and/or post treatment study follow-up, and entered on the appropriate CRF page. In the event that vital status (whether the subject is alive or dead) is being measured, publicly available information should be used to determine vital status only as appropriately directed in accordance with local law.

3.6.2 Lost to Follow-Up

All reasonable efforts must be made to locate subjects to determine and report their ongoing status. This includes follow-up with persons authorized by the subject as noted above. Lost to follow-up is defined by the inability to reach the subject after a minimum of three documented phone calls, faxes, or emails as well as lack of response by subject to one registered mail letter. All attempts should be documented in the subject's medical records. If it is determined that the subject has died, the site will use permissible local methods to obtain the date and cause of death.

If investigator's use of third-party representative to assist in the follow-up portion of the study has been included in the subject's informed consent, then the investigator may use a Sponsor-retained third-party representative to assist site staff with obtaining subject's contact information or other public vital status data necessary to complete the follow-up portion of the study. The site staff and representative will consult publicly available sources, such as public health registries and databases, in order to obtain updated contact information. If after all attempts, the subject remains lost to follow-up, then the last known alive date as determined by the investigator should be reported and documented in the subject's medical records.

4 STUDY DRUG

Study drug includes both Investigational [Medicinal] Product (IP/IMP) and Non-investigational [Medicinal] Product (Non-IP/Non-IMP) and can consist of the following:

Table 4-1: Study Drugs for CA209511

Product Description / Class and Dosage Form	Potency	Primary Packaging (Volume)/ Label Type	Secondary Packaging (Qty) /Label Type	Packaging/ Appearance	Storage Conditions (per label)
Nivolumab Solution for Injection ^a	100 mg (10 mg/mL)	10 mL per vial	5 or 10 vials per carton/ Open-label	Clear to opalescent colorless to pale yellow liquid. May contain particles	2° to 8°C. Protect from light and freezing
Ipilimumab	200 mg (5 mg/mL)	40 mL per vial/Open-label	4 vials per carton/Open-label	Clear to opalescent colorless to pale yellow liquid. May contain particles	2° to 8°C. Protect from light and freezing

^a Nivolumab is labeled as BMS-936558-01 Solution for Injection.

Pre-medications or medications used to treat in infusion reactions should be sourced by the investigative sites if available and permitted by local regulations.

4.1 Investigational Product

An investigational product, also known as investigational medicinal product in some regions, is defined a pharmaceutical form of an active substance or placebo being tested or used as a reference in a clinical study, including products already with a marketing authorization but used or assembled (formulated or packaged) differently than the authorized form, or used for an unauthorized indication, or when used to gain further information about the authorized form.

The investigational product should be stored in a secure area according to local regulations. It is the responsibility of the investigator to ensure that investigational product is only dispensed to study subjects. The investigational product must be dispensed only from official study sites by authorized personnel according to local regulations.

In this protocol, investigational products are:

- Nivolumab
- Ipilimumab

4.2 Non-investigational Product

Other medications used as support or escape medication for preventative, diagnostic, or therapeutic reasons, as components of the standard of care for a given diagnosis, may be considered as non-investigational products.

4.3 Storage and Dispensing

The product storage manager should ensure that the study drug is stored in accordance with the environmental conditions (temperature, light, and humidity) as determined by BMS. If concerns regarding the quality or appearance of the study drug arise, the study drug should not be dispensed and contact BMS immediately.

Study drug not supplied by BMS will be stored in accordance with the package insert.

Investigational product documentation (whether supplied by BMS or not) must be maintained that includes all processes required to ensure drug is accurately administered. This includes documentation of drug storage, administration and, as applicable, storage temperatures, reconstitution, and use of required processes (eg, required diluents, administration sets).

4.3.1 Part 1 Study Drug Administration (Combination Portion)

In the nivolumab plus ipilimumab combination portion, nivolumab is to be administered first. Subjects should receive nivolumab at a dose of 3 mg/kg (Arm A) or 1 mg/kg (Arm B) as a 30-minute IV infusion, on Day 1 of each treatment cycle every 3 weeks for 4 doses or until progression, unacceptable toxicity, withdrawal of consent, or the study ends, whichever occurs first.

The nivolumab infusion must be promptly followed by a saline flush to clear the line of nivolumab before starting the next infusion.

The second infusion in the combination cohort will always be ipilimumab, and will start approximately 30 minutes after completion of the nivolumab infusion and the infusion line has been flushed, filters changed and the patient has been observed to ensure no infusion reaction has occurred.

Subjects should receive ipilimumab at a dose of 1 mg/kg (Arm A) or at a dose of 3 mg/kg (Arm B) as a 30-minute IV infusion, on Day 1 of each treatment cycle every 3 weeks (within 3 calendar days of scheduled date) for 4 doses or until progression, unacceptable toxicity, withdrawal of consent, or the study ends, whichever occurs first.

The risk/benefit profile for nivolumab has primarily been investigated using a 60-minute infusion and for ipilimumab a 90-minute infusion. Long infusion times place a burden on patients and treatment centers. Establishing that these agents can be safely administered using shorter infusion times will diminish some of this burden. Previous clinical studies of nivolumab have used 60-minute infusion duration and for ipilimumab 90-minute. Both nivolumab and ipilimumab have been administered safely at doses ranging up to 10 mg/kg over these treatment durations. Overall, infusion reactions including high-grade hypersensitivity reactions have been uncommon across multiple clinical studies, and all have been managed by following the safety algorithms. Infusion duration of 30 minutes for 3 mg/kg nivolumab (30% of the dose provided at 10 mg/kg) is not expected to present any safety concerns compared with the prior experience at 10 mg/kg nivolumab dose infused over the 60-minute duration. Similarly, shortened infusion duration of 30 minutes for ipilimumab is not expected to present additional safety concerns.²⁴

Both agents given as single agent is uncommonly associated with infusion reactions, incidence less than 1% for ipilimumab (Yervoy® FDA Label) and for nivolumab 3%.⁹ In the CA209069 study, hypersensitivity/infusion reactions were listed as 3.2% for the combination and 2.2% for ipilimumab. No Grade 3 or Grade 4 hypersensitivity/infusion reactions were observed in either the combination or single agent ipilimumab treatment groups.²⁵

Subjects should be carefully monitored for infusion reactions during nivolumab/ipilimumab administration. If an acute infusion reaction is noted, subjects should be managed according to [Section 4.4](#).

The **pharmacy manual** includes detailed instructions for study medication preparation.

Dosing calculations should be based on the body weight assessed at screening. It is not necessary to re-calculate subsequent doses if the subject weight is within 10% of the weight used to calculate the previous dose. All doses should be rounded to the nearest milligram.

During Part 1, subjects may be dosed no less than 19 days between doses. If dosing is delayed, both nivolumab and ipilimumab must be delayed together. If dosing is resumed after a delay, both nivolumab and ipilimumab must be resumed on the same day.

Detailed instructions for dilution and infusion of nivolumab/ipilimumab injection may be provided in the pharmacy binder, pharmacy reference sheet or current investigator brochure.^{23,26} Care must

be taken to assure sterility of the prepared solution as the product does not contain any antimicrobial preservative or bacteriostatic agent.

4.3.2 Part 2 Study Drug Administration (Maintenance)

Starting 6 weeks after the last co-administered dose in Part 1, subjects will be administered a flat dose 480 mg nivolumab IV as a 30-minute IV infusion every 4 weeks (Q4W) (\pm 3 days) until unacceptable toxicity or disease progression, up to a maximum of 2 years treatment.

Subjects may be dosed up to 3 days after the scheduled date if necessary. Subsequent dosing should be based on the actual date of administration of the previous dose of drug. Every effort should be made to adhere to protocol treatment schedule of administration of nivolumab every 4 weeks in the maintenance phase. In extenuating circumstances in which the patient cannot make the dosing schedule within the 3-day window, BMS Monitor should be contacted.

For details on prepared drug storage, preparation, and administration, please refer to the BMS-936558 (nivolumab) IB, the ipilimumab IB and/or pharmacy reference sheets.

4.4 Method of Assigning Subject Identification

CA209511 is a randomized, double-blind study. After the subject's initial eligibility is established and informed consent has been obtained, the subject must be enrolled into the study by accessing an Interactive Response Technologies web-based system (IRT) to obtain the subject number. Every subject that signs the informed consent form must be assigned a subject number in IRT. Specific instructions for using IRT will be provided to the investigational site in a separate document. The investigator or designee will register the subject for enrollment by following the enrollment procedures established by BMS. The following information is required for enrollment:

- Date that informed consent was obtained
- Date of birth
- Gender at birth.

Once enrolled in IRT, enrolled subjects that have met all eligibility criteria will be ready to be randomized through the IRT. The following information is required for subject randomization:

- Subject number
- Date of birth
- PD-L1 expression level (PD-L1 \geq 5% expression vs PD-L1 $<$ 5% expression/indeterminate) entered by vendor
- M Stage at screening (See [Appendix 4](#)).

Subjects meeting all eligibility criteria will randomize 1:1 ratio to Arm A (N3I1) or Arm B (N1I3) and stratified by the following factors:

- PD-L1 expression
- M stage.

The randomization procedures will be carried out via permuted blocks within each stratum. The exact procedures for using the IRT will be detailed in the IRT manual.

4.4.1 Dose Delay Criteria

Regardless of whether or not the event is attributed to nivolumab, ipilimumab, or both, all study drugs must be delayed until treatment can resume (See Section 4.4.3). Tumor assessments for all subjects should continue as per protocol even if dosing is delayed.

Nivolumab and ipilimumab administration should be delayed for the following:

- Grade ≥ 2 non-skin, drug-related adverse event, with the exception of fatigue or laboratory abnormalities that do not require a treatment delay.
- Grade 2 drug-related creatinine, AST, ALT or Total Bilirubin abnormalities
- Grade 3 skin, drug-related adverse event
- Grade 3 drug-related laboratory abnormality, with the following exceptions :
 - Grade 3 lymphopenia does not require dose delay
 - If a subject has a baseline AST, ALT or total bilirubin that is within normal limits, delay dosing for drug-related Grade ≥ 2 toxicity
 - Grade ≥ 3 AST, ALT, or total bilirubin will require discontinuation
 - Any Grade ≥ 3 drug-related amylase or lipase abnormality that is not associated with symptoms or clinical manifestations of pancreatitis does not require dose delay.
- Any adverse event, laboratory abnormality, or intercurrent illness which, in the judgment of the investigator, warrants delaying the dose of study medication.

Subjects requiring delay should be re-evaluated weekly or more frequently if clinically indicated and resume dosing when re-treatment criteria are met.

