4.4.3 Criteria to Resume Treatment

Subjects should resume treatment with nivolumab and ipilimumab in both arms A and B given the blinded nature of the study when the drug-related AE(s) resolve(s) to Grade ≤ 1 or baseline, with the following exceptions:

- Subjects may resume treatment in the presence of Grade 2 fatigue
- Subjects who have not experienced a Grade 3 drug-related skin AE may resume treatment in the presence of Grade 2 skin toxicity
- Subjects with Grade 2 AST/ALT or total bilirubin may resume treatment when laboratory values return to baseline and management with corticoids, if needed, is completed.
- Subjects with combined Grade 2 AST/ALT AND total bilirubin values meeting discontinuation parameters (Section 4.4.1) should have treatment permanently discontinued

- Drug-related pulmonary toxicity, diarrhea, or colitis must have resolved to baseline before treatment is resumed. Subjects with persistent Grade 1 pneumonitis after completion of a steroid taper over at least 1 month may be eligible for retreatment if discussed with and approved by the BMS Medical Monitor.
- Drug-related endocrinopathies adequately controlled with only physiologic hormone replacement may resume treatment after consultation with the BMS Medical Monitor. Adrenal insufficiency requires discontinuation regardless of control with hormone replacement.

If the criteria to resume treatment are met, the subject should restart treatment at the next scheduled time point per protocol. However, if the treatment is delayed past the next scheduled time point per protocol, the next scheduled time point will be delayed until dosing resumes.

If treatment is delayed > 6 weeks, the subject must be permanently discontinued from study therapy, except as specified in [Section 4.4.1](#).

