4.4.4 Discontinuation Criteria

All discontinuation criteria apply for nivolumab and ipilimumab in both Arms A and B (during Part 1) given the blinded nature of this study.

Treatment should be permanently discontinued for the following:

- Any Grade 2 drug-related uveitis, eye pain or blurred vision that does not respond to topical therapy and does not improve to Grade 1 severity within the re-treatment period OR requires systemic treatment.
- Any Grade 3 non-skin, drug-related adverse event lasting > 7 days or recurs, with the following exceptions for laboratory abnormalities, drug-related uveitis, pneumonitis, bronchospasm, diarrhea, hypersensitivity reactions, infusion reactions and endocrinopathies:
 - Grade 3 drug-related uveitis, pneumonitis, bronchospasm, diarrhea, colitis, neurologic toxicity, hypersensitivity reaction, or infusion reaction of any duration requires discontinuation
 - Grade 3 drug-related endocrinopathies adequately controlled with only physiologic hormone replacement do not require discontinuation. Adrenal insufficiency requires discontinuation, regardless of control with hormone replacement.
 - Grade 3 drug-related laboratory abnormalities do not require treatment discontinuation except:
 - Grade 3 drug-related thrombocytopenia > 7 days or associated with bleeding requires discontinuation
 - Any drug-related liver function test (LFT) abnormality that meets the following criteria require discontinuation:
 - Grade ≥ 3 drug-related AST/ALT or Total Bilirubin abnormality
 - Concurrent AST or ALT > 3 x ULN and total bilirubin > 2 x ULN
- In most cases of Grade 3 AST or ALT elevation, study drugs) will be permanently discontinued. If the investigator determines a possible favorable risk/benefit ratio that warrants

continuation of study drug(s), a discussion between the investigator and the BMS Medical Monitor/designee must occur.

- Any Grade 4 drug-related adverse event or laboratory abnormality (including, but not limited to creatinine, AST, ALT, or total bilirubin), except for the following events which do not require discontinuation:
 - Grade 4 neutropenia \leq 7 days
 - Grade 4 lymphopenia or leucopenia
 - Isolated Grade 4 amylase or lipase abnormalities that are not associated with symptoms or clinical manifestations of pancreatitis.
 - Isolated Grade 4 electrolyte imbalances/abnormalities that are not associated with clinical sequelae and are corrected with supplementation/appropriate management within 72 hours of their onset

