 - Grade 4 drug-related endocrinopathy adverse events, such as hyper- or hypothyroidism, or glucose intolerance, which resolve or are adequately controlled with physiologic hormone replacement (corticosteroids, thyroid hormones) or glucose-controlling agents, respectively, may not require discontinuation after discussion with and approval from the BMS Medical Monitor.
- Any event that leads to delay in dosing lasting $>$ 6 weeks from the previous dose requires discontinuation, with the following exceptions:
 - Dosing delays to allow for prolonged steroid tapers to manage drug-related adverse events are allowed.
 - Dosing delays lasting $>$ 6 weeks from the previous dose that occur for non-drug-related reasons may be allowed if approved by the BMS medical monitor.
- Prior to re-initiating treatment in a subject with a dosing delay lasting $>$ 6 weeks, the BMS medical monitor must be consulted. Tumor assessments should continue as per protocol even if dosing is delayed. Periodic study visits to assess safety and laboratory studies should also continue every 6 weeks or more frequently if clinically indicated during such dosing delays.
- Any adverse event, laboratory abnormality, or intercurrent illness which, in the judgment of the Investigator, presents a substantial clinical risk to the subject with continued nivolumab dosing.

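### Section 4.4.1 excepts fatigue from the dose-delay rule without a grade limit, so a short first Grade 3 fatigue episode is held only by investigator judgment, although 4.4.3 does not allow restart at Grade 3

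*Protocol*

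**What the plan says.** Three protocol sections govern a toxicity at a dosing visit.

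- **4.4.1 (when to delay).** Drug-related non-skin events of Grade 2 or higher require a delay, "with the exception of fatigue or laboratory abnormalities that do not require a treatment delay". The two Grade 3 triggers cover skin events and laboratory abnormalities. A final bullet covers any event that, "in the judgment of the investigator, warrants delaying the dose of study medication". Delayed subjects are re-evaluated at least weekly and "resume dosing when re-treatment criteria are met".
- **4.4.3 (when to resume).** The general threshold is Grade 1 or lower, or baseline. For fatigue there is one relaxation: "Subjects may resume treatment in the presence of Grade 2 fatigue". If treatment is delayed more than 6 weeks, "the subject must be permanently discontinued from study therapy", apart from a cross-referenced exception.
- **4.4.4 (when to stop).** Permanent discontinuation applies to "Any Grade 3 non-skin, drug-related adverse event lasting" more than 7 days, or recurring. Some Grade 3 events, such as pneumonitis and colitis, require a stop at any duration; fatigue is not among them. A separate bullet says that a delay of more than "6 weeks from the previous dose requires discontinuation, with the following exceptions". One exception reads: "Dosing delays to allow for prolonged steroid tapers to manage drug-related adverse events are allowed". The other covers non-drug-related delays that the medical monitor approves.

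Protocol 4.3.1 (in the ipilimumab instruction) and 4.3.2 allow dosing up to 3 days after the scheduled date. SAP 7.4.2.1 counts a dose as delayed only beyond 3 days.

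**The concern.** The delay and resume rules do not match for fatigue. Grade 3 fatigue blocks a restart once a delay has begun, but it is not a mandatory reason to begin one.

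Other parts of 4.4.1 suggest an omission. Where the section means to spare a Grade 3 finding from delay, it names the grade, as it does for lymphopenia and for amylase or lipase changes without symptoms. The fatigue exception names none, while the matching resume rule names Grade 2.

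Delay is also the only step between a full dose and a permanent stop, because dose reductions (Protocol 4.4.2) and dose omissions (SAP 7.4.2.5) are not permitted. What is at stake is a subject receiving a full dose during current Grade 3 drug-related fatigue, and sites differing on whether to give it.

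**Working it through.** The plan gives no figure on this point to reproduce. The check applies each rule in turn to one case: a first drug-related Grade 3 fatigue episode, lasting 7 days or less, still present when the 3-day window closes.

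| Rule | Result |
|---|---|
| 4.4.1, Grade 2 or higher non-skin | Fatigue excepted, no grade stated |
| 4.4.1, Grade 3 skin | Not applicable |
| 4.4.1, Grade 3 laboratory | Not applicable |
| 4.4.4, Grade 3 over 7 days or recurring | Not met |
| 4.4.4, Grade 3 stop at any duration | Fatigue not listed |
| 4.4.1, 4.4.4 and 3.5, investigator judgment | The only route to a hold or stop |
| 4.4.3, restart if held | Not until Grade 2 or lower, or baseline |

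**Cases outside the gap.** An episode that clears within 3 days can be waited out inside the window. One that lasts more than 7 days or recurs meets the 4.4.4 stop. Because a second Grade 3 episode counts as recurrence, each subject can meet the gap in one episode only.

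**Length of a hold if the rule were tightened.** Take fatigue present on the scheduled day, with no earlier postponement:

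- End of episode: at most 7 days after the scheduled day.
- Past the window: 7 − 3 = 4 days.

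Time since the previous dose (dosing interval + 7 days), against the 4.4.4 limit of 6 × 7 = 42 days:

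- Part 1: 21 + 7 = 28 days, under 42.
- Between Part 2 doses: 28 + 7 = 35 days, under 42.
- Cycle 5, due 6 × 7 = 42 days after the last combination dose: 42 + 7 = 49 days, which is 7 over.

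Weekly re-evaluation may add days. One further week gives 35 days in Part 1 and 42 days between Part 2 doses, neither of which is more than 42. These figures assume that dosing resumes once the criteria are met, as 4.4.1 says. The reference in 4.4.3 to the next scheduled time point is less clear, but the gap does not depend on it.

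**Counting in the primary endpoint** (Protocol 8.3.1: onset within 30 days of the last dose). Fatigue present on the scheduled day began at most 21 days after the previous dose in Part 1, or 28 days between Part 2 doses, so it counts whether or not the dose is held. At Cycle 5, an episode of 7 days or less that outlasts the window (42 + 3 = day 45) began on about day 45 − 7 = 38 or later. That is outside 30 days of the last combination dose, so it counts only if Cycle 5 is given.

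**The case against.** The strongest reply is that the sections should be read together. Section 4.4.1 opens by pointing to 4.4.3, where Grade 2 is the highest fatigue grade named as tolerable, so Grade 2 is the evident intent. The words about not requiring a delay could also attach to fatigue. Investigator judgment can hold or stop treatment under 4.4.1, 4.4.4 and 3.5, and most investigators would probably hold a dose in this case.

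Much of this stands. A reader might infer that the protocol authorises full dosing in Grade 3 fatigue. It does not: 4.4.1 lists reasons to delay and is silent on this case, and the judgment clauses remain available. Grade 2 is probably what was meant.

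It does not close the gap. The pointer to 4.4.3 says when a delayed subject may resume; it does not create a trigger for delay. If the qualifying words also govern fatigue, the exception becomes circular and still gives no grade. The judgment clauses set no common threshold. Fatigue is also not among the seven groups with management algorithms listed in 4.4.6.

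**Conclusion.** The mismatch is real and narrow. As worded, the exception removes one Grade 3 drug-related toxicity from the mandatory hold, and neither the resume rule nor the judgment clauses restore it. This is a minor patient-safety and consistency correction.

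Two stronger readings should be avoided.

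- A reader might infer that every dose after the first adds exposure to the gap. The recurrence rule limits it to one episode per subject.
- A reader might infer a threat to the trial's comparison. The delay rules apply equally to both blinded arms (Protocol 4.4.2), and power, alpha and sample size are unchanged.

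The number of subjects affected cannot be derived, because the documents give no Grade 3 fatigue incidence. The conclusion rests on the text of 4.4.1, 4.4.3 and 4.4.4. The Appendix 3 algorithms were not available for review.

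**What to change.** In the Grade 2 or higher non-skin bullet of 4.4.1, insert *Grade 2* immediately before *fatigue*. Leave 4.4.3 and 4.4.4 unchanged. Grade 3 drug-related fatigue then requires a hold, and the delay rule agrees with the restart rule.

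The cost is one wording change in an amendment and an occasional short hold. No new procedure is needed, since weekly re-evaluation of delayed subjects is already required.

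The downside is at Cycle 5. Because that dose is due 6 weeks after the last combination dose, a mandatory fatigue hold there can meet the 4.4.4 stop for delays of more than 6 weeks from the previous dose. Holds there for other drug-related events already face this, apart from steroid tapers. A subject stopped in this way would also not have that episode counted in the primary endpoint, for the reason shown in the working. Moving the Cycle 5 clock would loosen the stop for every adverse event at that visit, so it is a separate decision for the sponsor and not part of this fix.
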